Endpoints and analysis: The primary endpoint of the study will be the development of sustained unresponsiveness to a 7444 mg egg white protein OFC followed by open consumption of a whole egg, 8-10 weeks after discontinuing 2 years of daily Baked Egg or Egg OIT. OFCs will be conducted in a supervised setting and safety parameters will be carefully monitored.

Individuals off therapy for 8-10 weeks, successfully demonstrating consumption of 7444 mg egg white protein OFC without dose-limiting symptoms followed by consuming a whole egg will be considered "successes." All others will be considered "failures" with respect to this endpoint. Among all subjects randomized, the number of subjects on each treatment successfully demonstrating sustained unresponsiveness will be compared to those failing to tolerate this quantity by Chi-square analysis.

Expected outcome/potential limitations: The expected outcome is that 40% of Baked Egg vs. 70% of Egg OIT subjects will tolerate 7444 mg egg white protein OFC, 8-10 weeks after discontinuing Egg OIT or Baked Egg products. The primary limitation to the study is the possibility that we have over-estimated the number of subjects who will tolerate the therapies or subjects do not adhere to dietary restrictions.

Secondary Objectives:

1. Determine the percentage of subjects who can successfully consume without dose limiting symptoms at least 4444 mg egg white protein of a 7444 mg egg white protein OFC after the initial desensitization phase of approximately 1 year of the study and at 2 years.

Rationale: Subjects allergic to egg often have accidental allergic reactions to small amounts of egg in other foods. Generally, the amount of egg causing these accidental allergic reactions is less than 500 mg of egg protein. Previous studies suggest that the continuous administration of a food allergen leads to a "desensitized" state in which an allergic subject will be unresponsive to the ingestion of a food allergen as long as they continue to ingest a small amount of the food on a daily basis.⁸⁰ Food challenges of egg white solid can be done to determine if accidental ingestions of typical amounts of egg could occur without adverse effects.

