5 SAMPLE SIZE CONSIDERATIONS

The sample size target for the randomized portion of the study is 96 individuals with 1:1 random assignment to Baked Egg and Egg OIT. The sample size was selected to determine whether a difference exists between the treatment groups in the primary endpoint rate for the sustained unresponsiveness-focused portion of the study. Specifically, the sample was designed to have 85% power to detect with a two-sided 5% level test, a difference between a 40% and 70% sustained unresponsiveness rate. While a small dropout rate may occur, we will use all randomized cases who initiate treatment in the intent-to-treat analysis of the primary endpoint; failures associated with noncompliance are include in the denominator for event rates above. This sample size is sufficient to address the secondary endpoint of the desensitization components of the study for event rate differences of comparable size.

The subset of individuals who are not baked egg tolerant at baseline comprise a selected group of individuals where Egg OIT will be examined. The size of the group will be capped at approximately 40 subjects. The study cohort should be useful for both clinical and mechanistic study with approximately 40 such individuals enrolled. The 2 year sustained unresponsiveness rate will be compared to historical experience as well as the protocol's randomized Egg OIT arm. Mechanistic studies will be examined to determine if baseline immune system responses are similar in both Egg OIT groups. Immune parameter

changes will be examined to determine if tolerant and non-tolerant cases have response profiles that are parallel for the 2 strata.

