6.8 Multiple Comparisons/Multiplicity

A two-sided significance level of 0.05 will be used for primary, secondary, and safety endpoints. For planned mechanistic analyses (e.g., temporal changes, differences between responders and non-responders) a p-value of 0.01 will be used to control for the multiplicity of tests.

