8.3.3 Exploratory Efficacy Analyses

Although not specified in the protocol, changes in SCD from baseline to each protocol OFC are of scientific interest. The change in SCD will be compared between treatment using the Wilcoxon Rank Sum test to do pairwise comparisons between treatment groups. Effects of age will also be explored.

Analyses will also consider participants who successfully passed the desensitization OFCs to 7444 mg of egg white protein at the Week 52 and Year 2 OFCs. Comparisons between groups will be assessed in a similar fashion to the secondary endpoints above.

Clinical and immunological predictors of sustained unresponsiveness are of great scientific and medical interest. Of particular interest is the effect of age on treated effect and clinical outcomes. Logistic regression may be used to identify predictors of clinical response (i.e., desensitization and/or sustained unresponsiveness). Predictors will be incorporated into models adjusting for treatment where possible. Transformations will be implemented as appropriate and model fit will be assessed using the Hosmer-Lemeshow goodness of fit test. Area under the curve (AUC) may be used as an assessment of predictor strength. If the number of successes permits, multivariable models may be fit and stepwise regression techniques applied to identify important predictors or combinations of predictors.

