11.2 Immunoglobulin Results

Egg specific IgE, IgG4, and total IgE are measured at baseline, Week 12, Week 24, Week 52, Month 16, Month 20, Year 2, Month 26 and Month 30. Percent egg-specific IgE and IgG4/IgE ratio will be calculated as described in Section 3.3 above. Immunoglobulin results and changes from baseline will be reported at each of these timepoints by treatment group and by Year 2 sustained unresponsiveness status.

Change from baseline will be compared between treatment groups and by Year 2 sustained unresponsiveness status using the Wilcoxon Rank-Sum test to do pairwise group comparisons. A repeated measures model will be fit using the post-baseline timepoints except for the Month 30 visit (which is after the final OFC) and adjusted for baseline value, treatment or Year 2 sustained unresponsiveness status, and visit to assess any treatment effect or Year 2 sustained unresponsiveness effect on immunoglobulin measures. An appropriate covariance structure will be selected (with preference given to unstructured models). If there are too few subjects who have completed the Year 2 sustained unresponsiveness OFC to allow for a reasonable model fit, the model may be adjusted accordingly.

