11.3 Activated Basophil Analysis

Activated basophil outcomes will be constructed as described in Section 3.3. Activated basophils will be measured at baseline, Week 12, Week 24, Week 52, Month 16, Month 20, Year 2, Month 26 and Month 30. Activated basophil results for each stimulation level and changes from baseline will be reported at each of these timepoints by treatment group and by Year 2 sustained unresponsiveness status.

Change from baseline will be compared between treatment groups and by Year 2 sustained unresponsiveness status using the Wilcoxon Rank-Sum test to do pairwise group comparisons. A repeated measures model will be fit using post-baseline timepoints except for the Month 30 visit (which is after the final OFC) and adjusted for baseline value, treatment or Year 2 sustained unresponsiveness status and visit to assess any treatment effect or Year 2 sustained unresponsiveness status effect on basophil measures. An appropriate covariance structure will be selected (with preference given to unstructured models). If there are too few subjects who have completed the Year 2 sustained unresponsiveness OFC to allow for a reasonable model fit, the model may be adjusted accordingly.

For each of the egg stimulant levels within each treatment group, a Signed Rank test will be done for the egg value minus IL-3 (negative control), the anti-IgE value (positive control) minus IL-3, and the anti-IgE value minus the egg value at each time point to see if these values are significantly different than zero. A significant difference for egg minus IL-3 or anti-IgE minus IL-3 would indicate a response to egg or to beads, respectively. A significant difference for anti-IgE minus egg would indicate that the response was significantly different for anti-IgE than for egg.

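### SAP 11.2–11.4: on the natural reading, tests of markers by sustained-unresponsiveness status do not adjust for treatment group, so treatment-shifted markers are over-flagged if SU rates differ by group

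*SAP*

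**What the plan says.** SAP 11.2 plans two analyses of immunoglobulins by SU status. The first is a rank test, in a sentence that begins "Change from baseline will be compared between treatment groups and by Year 2 sustained unresponsiveness status using the Wilcoxon Rank-Sum test to do pairwise group". The second is a repeated-measures model "adjusted for baseline value, treatment or Year 2 sustained unresponsiveness status, and visit". SAP 11.3 (basophils) has the model "adjusted for baseline value, treatment or Year 2 sustained unresponsiveness status and visit", and SAP 11.4 (flow cytometry) follows the same pattern. None of these sections mentions stratifying the SU-status rank test by treatment.

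SAP 11.1 (skin prick test) differs. Its optional model lists baseline, treatment and visit. It leaves SU status out of the covariates, although the model is meant to assess an SU-status effect.

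SAP 6.8 covers responder versus non-responder comparisons among the mechanistic tests: "a p-value of 0.01 will be used to control for the multiplicity of tests". Protocol 9.5 calls the mechanistic work exploratory. For the optional logistic models of clinical response, SAP 8.3.3 says: "Predictors will be incorporated into models adjusting for treatment where possible".

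The design figures are in SAP 5, "The sample size target for the randomized portion of the study is 96 individuals with 1:1 random assignment to Baked Egg and Egg OIT", and Protocol 2.1, "The expected outcome is that 40% of Baked Egg vs. 70% of Egg OIT subjects will tolerate 7444 mg egg white protein OFC".

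**The concern.** The trial is built on a large difference in SU between arms. If treatment also moves a marker, treatment is a common cause of marker change and SU. A comparison by SU status that ignores treatment then compares groups with different treatment mixes, and it can show a difference when marker and SU are unrelated within each arm.

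Protocol 2.1 (tertiary objectives) raises the stakes. It first identifies the assay endpoints that differ by treatment and then asks whether immune states predict the tolerized or desensitized state. Treatment-shifted markers are the ones exposed to this problem. The Protocol's summary of the previous egg OIT trial (1.1) reports a rise in IgG4 and a fall in basophil activation on OIT, so shifts are plausible. Their size relative to Baked Egg is not given.

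What is at stake is the interpretation of SU associations, mainly tertiary hypothesis 1 (Th2, Treg and Tfh cells and SU).

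**Working it through.** **Inputs from the documents.** 96 randomized 1:1, so 48 per arm; SU 40% versus 70%; two-sided 5% for the primary test; 85% power; 0.01 for mechanistic tests; about 40 in eOIT-Assigned.

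**Assumptions not in the documents.** The treatment shift d in SD units, a normally distributed marker, complete data, one summary value per subject in place of the full repeated-measures model, and the SU rate in eOIT-Assigned.

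**The plan's own figure.** With pooled variance and no continuity correction, z = [0.30·√48 − 1.960·√(2·0.55·0.45)] / √(0.24 + 0.21) = (2.078 − 1.379)/0.671 = 1.043, so power is 85.1%. The stated 85% is reproduced.

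**Treatment mix by SU status at 40%/70%.**
- SU subjects: 48·(0.4 + 0.7) = 52.8, of whom Egg OIT makes up 0.7/1.1 = 63.6%.
- Non-SU subjects: 48·(0.6 + 0.3) = 43.2, of whom Egg OIT makes up 0.3/0.9 = 33.3%.
- A shift of d SD therefore appears as an SU difference of (0.636 − 0.333)·d = 0.303·d, with no within-arm link.

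**Approximate rejection rate at two-sided 0.01 (critical value 2.576).** SE = √[(1 + d²·0.636·0.364)/52.8 + (1 + d²·0.333·0.667)/43.2].
- d = 0.5: 0.152/0.211 = 0.718, rejection about 3.2%.
- d = 1: 0.303/0.227 = 1.334, rejection about 10.7%.
- d = 2: 0.606/0.283 = 2.140, rejection about 33%.

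**Simulation, two randomized arms, marker independent of SU within arm, rejection at 0.01** (3,000–5,000 trials per setting where the run count is recorded):

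| Analysis by SU status | 0.5 SD | 1 SD | 2 SD |
|---|---|---|---|
| Wilcoxon, unstratified | 3.1–3.2% | 9.8–11.1% | 32–34% |
| Model, SU only, no baseline covariate | 3.3% | 10.2% | 30.7% |
| Model, SU only, baseline correlation 0.5 | 3.7–4.1% | 12.8–14.3% | 36–37% |
| Model, SU and treatment, no baseline covariate | 1.0% | 1.1% | 0.9% |
| Wilcoxon stratified by treatment (van Elteren) | 1.0% | 0.8% | 0.7% |

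With the baseline covariate, adding treatment also gives about 1%. Adjusting for baseline, as the SAP does, reduces residual variance and so makes the spurious difference easier to detect.

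**When SU rates are closer.** At 30% versus 40% the mix differs by only 0.4/0.7 − 0.6/1.3 = 0.110. The simulated Wilcoxon rate is 1.7% at 1 SD and 3.3% at 2 SD. With 27.5% in both arms it stays at about 1% for every d.

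**If eOIT-Assigned is pooled in** (40 subjects, given the same marker shift as randomized Egg OIT). For assumed SU rates of 20%, 30% and 50% in that group, the share on Egg OIT differs between SU and non-SU subjects as follows:
- 20%: 41.6/60.8 − 46.4/75.2 = 0.067.
- 30%: 45.6/64.8 − 42.4/71.2 = 0.108.
- 50%: 53.6/72.8 − 34.4/63.2 = 0.192.

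The simulated Wilcoxon rates at 1 SD are 1.4%, 2.0% and 5.4%. With treatment group in the analysis, all three-group runs give 0.7–1.2%.

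**The case against.** The strongest objection concerns the null hypothesis. If treatment drives both marker and SU, the two really are associated across the pooled arms, so a pooled Wilcoxon that rejects makes no type I error for its own null. Protocol 2.1 plans comparisons of those who do and do not achieve SU by univariate nonparametric methods, and its overall hypothesis makes immune change a step on the path from therapy to SU. This stands to a point: the pooled comparison is legitimate as description. It cannot support a statement that a marker is linked to SU beyond its link to treatment. The percentages above are errors against that within-arm null.

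Second, the word *or* in SAP 11.2–11.4 most naturally means two separate models but does not settle it, and the SAP does not say which groups enter the SU comparison. Both points stand; they are reasons to state the model explicitly.

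Third, SAP 8.3.3 already offers treatment-adjusted predictor models. A reader might infer that Section 11 contradicts 8.3.3. It does not: 8.3.3 models clinical response as the outcome, Section 11 models the marker, and the two can coexist. But the 8.3.3 models are optional and do not repair the tests in Section 11.

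Fourth, the work is exploratory. That limits the weight of the point without removing it, since SAP 6.8 sets a 0.01 level for responder comparisons as a safeguard.

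**Conclusion.** The point holds for the SU-status models in SAP 11.2–11.4, on their natural reading, and for the unstratified SU-status Wilcoxon tests in 11.1–11.4. At the design SU rates, with two randomized arms of 48, the 0.01 test flags a treatment-shifted marker unrelated to SU within arm in about 3–4%, 10–14% and 31–37% of trials at shifts of 0.5, 1 and 2 SD. The shifts are assumptions, and the size also depends on the SU rates and on which groups are pooled.

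Three stronger readings are not supported:
- A reader might infer that any marker moved by treatment will look like a marker of SU. Inflation also needs SU rates that differ between groups, and even at 40%/70% a 1 SD shift is flagged in only about one trial in seven to ten.
- A reader might infer that every mechanistic model omits treatment. The optional skin-test model in 11.1 lists it; what it lacks is SU status.
- A reader might infer that tertiary hypotheses 1–3 are all compromised. Hypothesis 2 concerns desensitization, and hypothesis 3 concerns an epitope profile that SAP 11.1–11.4 do not analyse.

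The primary analysis and its power are unaffected.

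**What to change.** - **SAP 11.2–11.4:** put treatment group and SU status together in the model that estimates the SU-status effect.
- **SAP 11.1:** keep treatment in the optional model and add SU status.
- **Wilcoxon by SU status, 11.1–11.4:** stratify by treatment group (van Elteren is one option) or report within group. Label any pooled comparison descriptive.
- **Groups:** state whether eOIT-Assigned enters the SU-status comparisons.

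The cost is SAP wording and one extra model term (two indicators if all three groups are used). There is a small loss of precision because SU and treatment are correlated. At 40%/70% with equal arms, r² = 0.30²·0.25/(0.55·0.45) = 0.091, so the variance of the SU coefficient rises by a factor of 1/(1 − 0.091) = 1.10 for the same residual variance. That is about 5% on the standard error, partly offset when treatment explains marker variance.

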11.3 Activated Basophil Analysis

Activated basophil outcomes will be constructed as described in Section 3.3. Activated basophils will be measured at baseline, Week 12, Week 24, Week 52, Month 16, Month 20, Year 2, Month 26 and Month 30. Activated basophil results for each stimulation level and changes from baseline will be reported at each of these timepoints by treatment group and by Year 2 sustained unresponsiveness status.

Change from baseline will be compared between treatment groups and by Year 2 sustained unresponsiveness status using the Wilcoxon Rank-Sum test to do pairwise group comparisons. A repeated measures model will be fit using post-baseline timepoints except for the Month 30 visit (which is after the final OFC) and adjusted for baseline value, treatment or Year 2 sustained unresponsiveness status and visit to assess any treatment effect or Year 2 sustained unresponsiveness status effect on basophil measures. An appropriate covariance structure will be selected (with preference given to unstructured models). If there are too few subjects who have completed the Year 2 sustained unresponsiveness OFC to allow for a reasonable model fit, the model may be adjusted accordingly.

For each of the egg stimulant levels within each treatment group, a Signed Rank test will be done for the egg value minus IL-3 (negative control), the anti-IgE value (positive control) minus IL-3, and the anti-IgE value minus the egg value at each time point to see if these values are significantly different than zero. A significant difference for egg minus IL-3 or anti-IgE minus IL-3 would indicate a response to egg or to beads, respectively. A significant difference for anti-IgE minus egg would indicate that the response was significantly different for anti-IgE than for egg.

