Results: 55 subjects enrolled; 6/40 (15%) egg OIT and 2/15 (13.3%) placebo subjects withdrew before 24 months. After 10 months of therapy, 0/15 (0%) placebo and 22/40 (55%) egg OIT subjects were desensitized; after 22 months, 30/40 (75%) were desensitized. Egg OIT was then stopped for 4-6 weeks and subjects underwent another OFC; 11/40 (27.5%) egg OIT subjects passed this OFC achieved sustained unresponsiveness. Symptoms during year 1 of dosing were mild-moderate; 75% of 11,860 egg doses and 96% of 4018 placebo doses were symptom-free. Egg OIT treatment led to the following mechanistic changes: basophil activation declined from baseline to 22 months (p<0.001); prick skin test size declined (p=0.02); egg-specific IgG4 increased (p<0.001); egg-specific IgE declined (N.S.). Among egg OIT subjects, smaller PST size at 22 months was correlated with desensitization (p=0.009) and sustained unresponsiveness (p=0.005), as was change from baseline PST to the PST performed at 22 months (p=0.01).

Conclusions: These results establish that egg OIT can induce desensitization in most patients and sustained unresponsiveness in some. Reductions in basophil and mast cell activation and increases in IgG4 antibody indicate effective immunomodulation and may predict desensitization and sustained unresponsiveness.³⁸

Immunotherapy with heat-denatured (baked) egg protein

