For each of the planned assay points, we will compare treatment differences in the Egg OIT vs. Baked Egg treated subjects, and in those who achieve sustained unresponsiveness vs. those who fail to develop sustained unresponsiveness. We will assess each with univariate nonparametric statistics and where applicable repeated measure methods will be applied with suitable transformations as necessary.

Those assay endpoints with detected treatment differences will be considered Baked Egg or Egg-OIT affected endpoints. Subsequently, we will evaluate whether immune states, as measured by the mechanistic assays, are predictive of the tolerized and/or desensitized states.

Our hypotheses are based on the probability that Baked Egg therapy and Egg OIT will induce immunologic changes in egg-allergic subjects that will result initially in *desensitization* and eventually with prolonged administration, the development of sustained unresponsiveness to egg.

Hypothesis 1: The development of clinical sustained unresponsiveness to egg is associated with a reduction in allergen-specific Th2 effector cells, an increase in allergen-specific T regulatory (Treg) cells, and an induction of allergen-specific T follicular helper (Tfh) cells.

Antigen-specific CD4+ T cells can be identified by their upregulation of CD154 in response to short-term antigen re-stimulation *in vitro*. We expect that egg immunotherapy leading to sustained unresponsiveness will be associated with sustained changes in the adaptive immune response to egg. We anticipate that Th2 cells that provide T cell help to B cells in support of IgE class-switching will be lost, leading to the eventual decline in allergen-specific IgE. We anticipate that egg-specific Tregs will be induced, contributing to the suppression of the Th2 response. This is based on literature showing that children who have outgrown their milk allergy have increased CD4⁺ CD25⁺ cells after milk challenge, and that depletion of these cells enhances proliferation of milk-specific effector cells. In addition, we expect that boosting of IgG4 levels in response to immunotherapy will be associated with the expansion of egg-specific CD4⁺ T cells bearing markers of T follicular helper cells. We anticipate that these 3 changes participate in development of sustained unresponsiveness and will therefore correlate with clinical outcome.

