PBMCs will be isolated at baseline and timepoints throughout immunotherapy. PBMCs will be stimulated for 6 or 18 h with egg antigen, followed by flow cytometric analysis of T cell phenotype. Allergen-specific T cells will be identified as $CD3^+$, $CD4^+$, $CD154^+$ cells. Function of these antigen-specific T cells will be inferred by their expression of cytokines, chemokine receptors, and regulatory markers. For example, Th2 effector cells at baseline would be IL-4 and IL-13-positive, and express variable levels of the chemokine receptors CCR4 and CCR6 that confer homing specificity to the skin and mucosal sites, respectively. After immunotherapy, we hypothesize that we will observe an expansion of antigen-specific CD4+ T cells with a phenotype of CD25-high and CD127-low, with potential co-expression of IL-10 and IFN- γ . Furthermore, antigen-specific Tfh cells will be identified by expression of the chemokine receptor CXCR5, and we hypothesize that we will observe an expansion of antigenession of this population after immunotherapy, potentially co-expressing IL-10 but not Th2 cytokines. We hypothesize that this Tfh population would underlie the increase in IgG4 observed in response to immunotherapy.

Hypothesis 2: The development of the desensitized state to egg is associated with the down-regulation of basophils.

We hypothesize that the development of a "desensitized state" in egg-allergic subjects on Baked Egg therapy or Egg OIT will be associated with allergen-specific basophil hyporesponsiveness. Two clinical observations, suggesting potentially different mechanisms, support this hypothesis. The first is that in conditions of ongoing 'natural' antigen exposure, such as individuals chronically infected with helminths or food-allergic children regularly consuming an offending antigen (e.g., milk-allergic infant on milk-based formula), patients do not experience intense immediate hypersensitivity symptoms, though there is evidence of chronic low grade basophil and/or mast cell activation and 'spontaneous' histamine release.^{67,68,69} *In vivo* constitutive activation of basophils correlates with CD203c expression measured directly *ex vivo*.⁷⁰ The second observation is from drug sensitization studies, which similar to our protocol, achieved sustained unresponsiveness by administration of sub-threshold doses of antigen (hapten) followed by incremental increases. This has been shown to result in mast cell and basophil hyporesponsiveness.

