3.1 Study Objectives

The primary objective of the study is to determine in baked-egg tolerant, but egg-allergic, children whether daily baked egg therapy vs. daily oral administration of egg white solid escalated to a maximum of 2500 mg/day, increases sustained unresponsiveness as measured by a 7444 mg egg white protein OFC performed 8-10 weeks after therapy discontinuation by the 2 year time point.

Secondary objectives are to:

- 1. Determine the percentage of subjects who can successfully consume without dose limiting symptoms at least 4444 mg egg white protein of a 7444 mg egg white protein OFC after the initial desensitization phase of approximately 1 year of the study and at 2 years.
- 2. Determine the incidence of all serious adverse events.
- 3. Characterize unrestricted egg consumption after conclusion of treatment via long term follow-up.

Tertiary (mechanistic) objectives include testing the following hypotheses:

- 1. The development of clinical sustained unresponsiveness to egg is associated with a reduction in allergen-specific Th2 effector cells, an increase in allergen-specific T regulatory (Treg) cells, and an induction of allergen-specific T follicular helper (Tfh) cells.
- 2. The development of the desensitized state to egg is associated with the down-regulation of basophils.
- 3. The persistence of egg allergy is associated with an epitope-specific IgE antibody profile that is distinct from persons who lose their clinical allergy to egg.
- 4. Sustained unresponsiveness will be associated with a predictive transcriptional signature detectable in whole blood or allergen restimulated PBMCs.

While the above objectives have been framed in terms of the randomized comparison that is central to this study, individuals who comprise the Egg OIT assignment group will have endpoints similar to the randomized cases. The assignment group will be compared to the randomized arms and evaluated for sustained unresponsiveness, desensitization, safety and immune system function. It is anticipated that this group will have less desensitization and sustained unresponsiveness success than the randomized Egg OIT subjects. If supported by the results, it will be an objective to determine if immune parameter studies can help explain the differences.

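### SAP 11.3 has no committed comparison of basophil change by desensitization status, although the basophil hypothesis is about desensitization

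*SAP*

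**What the plan says.** SAP 3.1 states tertiary hypothesis 2 as: "The development of the desensitized state to egg is associated with the down-regulation of basophils". Protocol 2.1 states the same hypothesis for both therapies and adds, for the mechanistic assays in general, that "we will evaluate whether immune states, as measured by the mechanistic assays, are predictive of the tolerized and/or desensitized states". Protocol 8.2 and 9.5 also name desensitization, alongside sustained unresponsiveness, as an outcome to which the assays will be related.

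SAP 11.3 plans three things for activated basophils:

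- A rank-sum comparison: "Change from baseline will be compared between treatment groups and by Year 2 sustained unresponsiveness status".
- A repeated-measures model "to assess any treatment effect or Year 2 sustained unresponsiveness status effect on basophil measures".
- Stimulant contrasts: "For each of the egg stimulant levels within each treatment group, a Signed Rank test will be done". These compare egg, anti-IgE and IL-3 values and use no clinical outcome.

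Desensitization is a defined yes/no variable in SAP 3.3 (successfully consumed dose of at least 4444 mg). It is assessed at Week 52 and Year 2, when basophils are also sampled. It does not appear in SAP 11.3. SAP 8.3.3 mentions it as an option: "Logistic regression may be used to identify predictors of clinical response (i.e., desensitization and/or sustained unresponsiveness".

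**The concern.** The hypothesis names one clinical state and the planned basophil tests use another. The protocol's background keeps the two apart: it attributes desensitization mainly to mast cells and basophils, and longer-lasting tolerance presumably to T-cell effects. SU status is therefore not an obvious substitute.

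The grouping also mixes children by construction. Only those who pass the full 7444 mg challenge on therapy go on to the off-therapy challenge, and SAP 3.3 counts those who never attempt it as failures. A child who reaches 4444 mg but not 7444 mg at Year 2 is desensitized and yet in the SU comparison group. So is a child who passes on therapy and reacts after the break. If basophil suppression follows desensitization, both kinds of child pull the comparison group towards the SU group. A desensitization analysis chosen after the data are seen would be post hoc.

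**Working it through.** **The plan's own figure.** SAP section 5 gives 96 randomized, 1:1, 85% power, SU 40% vs 70%, two-sided 5%. With 48 per arm and no continuity correction, z = [0.30 - 1.96 × √(2 × 0.55 × 0.45/48)] / √[(0.24 + 0.21)/48] = (0.300 - 0.199)/0.0968 = 1.04, so power is 85.1%. The figure reproduces and is not in dispute. It supplies the planned pooled SU rate, S = (0.40 + 0.70)/2 = 0.55.

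**Other inputs.**

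- Earlier egg OIT trial (protocol 1.1): "after 22 months, 30/40 (75%) were desensitized", and 11/40 (27.5%) reached SU.
- Mechanistic significance level: 0.01 (SAP 6.8).
- D in this trial: not given. Protocol 2.1 expects only a majority, after 40 to 48 weeks, so 60%, 75% and 85% are assumed here.
- Marker shift: not given. Assumed 1 SD in desensitized children, with no further shift in SU children.

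**Formulas.** At Year 2, SU successes are a subset of the desensitized.

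- Share of desensitized children in the non-SU group: (D - S)/D.
- Share of the non-SU group that is desensitized: (D - S)/(1 - S).
- Share of the desensitization contrast that survives grouping by SU: 1 - (D - S)/(1 - S) = (1 - D)/(1 - S).

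At the earlier trial's counts, 30 - 11 = 19 children are desensitized without SU. That is 19/30 = 63% of the desensitized and 19/29 = 66% of the non-SU group, and 10/29 = 34% of the contrast is kept.

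**Results.** Power is for a simulated rank-sum test with N = 96, all sampled; figures move by a point or two between runs.

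| Rates | D | S | Desensitized who are non-SU | Non-SU who are desensitized | Contrast kept | Power by desensitization vs by SU |
|---|---|---|---|---|---|---|
| Planned, pooled | 60% | 55% | 8% | 11% | 89% | 98% vs 93% |
| Planned, pooled | 75% | 55% | 27% | 44% | 56% | 92% vs 44% |
| Planned, pooled | 85% | 55% | 35% | 67% | 33% | 76% vs 12% |
| Earlier trial | 75% | 27.5% | 63% | 66% | 34% | 93% vs 9% |

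**When would most desensitized children be non-SU?** (D - S)/D exceeds one half only if D > 2S. Pooled, that needs D > 110%, and in Egg OIT D > 140%, both impossible. In Baked Egg it needs D > 80%. Even at D = 100% the share is 1 - S: 45% pooled, 30% in Egg OIT, 60% in Baked Egg.

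**Missing children.** The power figures are upper bounds, because children off treatment may have no sample or challenge. In the earlier trial 6/40 withdrew and 10/40 were not desensitized. If as many as 6 of those 10 had no sample (an assumption), power by desensitization at the earlier trial's rates could fall from 93% to about 56% at N = 96. Power by SU falls too.

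**The case against.** The strongest reply is that the plan covers more than SAP 11.3. Protocol 9.5 says the mechanistic analysis strategies are given with each objective in section 2.1. There, the primary basophil analysis is egg-induced CD63+ against IL-3 alone, followed over time against baseline. Relating treatment success to CD63 suppression is secondary and conditional on being feasible. SAP 11.3 carries most of this over. SAP 6.4 says mechanistic factors will be used as predictors of clinical response, SAP 8.3.3 counts desensitization as such a response, SAP 6.8 lists responder comparisons among the planned mechanistic analyses, and SAP 12 leaves room for further detail.

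This stands against a reader's inference that the plan cannot address the hypothesis at all. It does not close the gap. SAP 6.4 and 6.8 name neither basophils nor desensitization, SAP 8.3.3 is optional and exploratory, and the analyses carried over from protocol 2.1 do not divide children by desensitization.

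A second reply concerns size. A reader might infer from the earlier trial that most desensitized children land in the comparison group and that power collapses to around 9%. This trial's planned SU rates do not support that for the pooled arms or for Egg OIT. The earlier trial also used a 4-6 week break rather than 8-10, and the protocol does not say its 30/40 used the 4444 mg criterion. Nor need the marker follow desensitization alone: in that trial a smaller skin test was associated with both desensitization (p=0.009) and SU (p=0.005). An extra shift in SU children would lessen the dilution.

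Third, the hypothesis is tertiary and protocol 9.5 calls the mechanistic work exploratory. That limits the weight of the point.

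**Conclusion.** The point holds in a limited form. The basophil hypothesis concerns desensitization, every outcome-based basophil test in SAP 11.3 uses Year 2 SU, and no committed basophil-by-desensitization analysis is specified elsewhere. Grouping by SU dilutes the contrast by an amount that depends on how far desensitization exceeds SU. At the planned pooled SU rate the loss is small if D is 60% (89% kept) and large if D is 85% (33% kept). These sizes rest on an assumed D, an assumed 1 SD shift tied to desensitization only, and complete sampling.

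A reader might also infer that a null result by SU status would count against the hypothesis. It should not, because that contrast is a different question, but the documents do not say it would be read that way. This is a cheap improvement to an exploratory analysis. It does not touch the primary endpoint.

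**What to change.** In SAP 11.3, add as the planned test of hypothesis 2: change from baseline in egg-induced %CD63+ basophils at Week 52 and at Year 2, compared by desensitization status (successfully consumed dose of at least 4444 mg) at that same visit, at the 0.01 level.

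- Adjust for or stratify by treatment group and pool across groups. Separate within-arm tests could leave very few non-desensitized children in a cell.
- Make the main comparison among children with both a basophil sample and an on-therapy challenge at that visit.
- Add a sensitivity analysis that counts children without a challenge as not desensitized, as SAP 3.3 does, using whatever samples exist.
- Keep the SU comparison, labelled as a separate question.

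The cost is about one paragraph and one table, with no new samples or visits. The small downside is one more family of exploratory tests.
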